ULN	upper limit of normal
US	United States of America
WHO	World Health Organization

4. Introduction

This statistical analysis plan (SAP) details comprehensive, technical specifications of the statistical analyses of the efficacy and safety data outlined and/or specified in the protocol amendment #2 dated 06 Dec 2017 of Study UBR-MD-04. Specifications of tables, figures, and data listings are contained in a separate document. The SAP for health economics and outcomes research (HEOR) data will be prepared separately.

This document is organized into 3 main sections:

1. Study overview
2. [Statistical Methodology and Study Endpoints](#)
3. [Data Handling and Analysis Conventions](#)

4.1 Study Design Summary

Structure: Multicenter, randomized, open-label, 52-week extension study; randomization to the ubrogepant arms (50 and 100 mg) will be blinded.

Duration: 52 weeks

Study Treatment Groups: usual care, ubrogepant 50 mg, or ubrogepant 100 mg

Controls: Not applicable

Dosage/Dose Regimen: Patients randomized to either of the ubrogepant arms will treat up to 8 migraine attacks (of any pain severity) every 4 weeks at home for a total 1 year. Patients have the option to take a second dose of ubrogepant if the patient has either a nonresponding migraine or a migraine recurrence. The second dose of ubrogepant will be identical to the first dose.

Patients randomized to the usual-care arm will be instructed to treat their migraine with medications that they routinely use to relieve a migraine attack.

Randomization: [REDACTED] Patients will be randomized (1:1:1) to 1 of the following 3 treatment groups: usual care, ubrogepant 50 mg, or ubrogepant 100 mg. The study is open-label; however, randomization to the ubrogepant arms (50 and 100 mg) will be blinded.

[REDACTED]

Number of Participants: Approximately 1200 patients will be randomized (400 patients per arm) from approximately 200 centers in the United States.

4.2 Study Objectives and Endpoints

[figure not shown]
Each study objective is presented with corresponding endpoint(s) below:

[figure not shown]
Table 4-1 Study Objectives and Corresponding Endpoints

Objectives	Endpoints

Primary
 
• [PO1] To evaluate the safety and tolerability of intermittent treatment with ubrogapant for the acute treatment of migraine over 1 year	
[REDACTED]
 
• [REDACTED]• [REDACTED]• [REDACTED]• [REDACTED]• [REDACTED]• [REDACTED]• [REDACTED]• [REDACTED]• [REDACTED]• [REDACTED]• [REDACTED]

Objectives	Endpoints
	

█ [REDACTED]
█ [REDACTED]
█ [REDACTED]
█ [REDACTED]
█ [REDACTED]
█ [REDACTED]
█ [REDACTED] 
Safety Assessments
 

• Adverse events (AE), clinical laboratory values, vital signs, electrocardiogram (ECG), physical examinations, and the Columbia–Suicide Severity Rating Scale (C-SSRS)

4.3 Schedule of Activities

5. Statistical Methodology and Study Endpoints

5.1 Statistical Methods Planned in the Protocol and Determination of Sample Size

This statistical analysis plan (SAP) will be approved prior to database lock. The SAP expands the statistical section of the protocol and contains a detailed description of methods to analyze data collected in the study. The text portion of the SAP will be included in the clinical study report (CSR) report as Appendix 16.1.9.

5.1.1 Statistical and Analytical Plans

Statistical analyses will be conducted using [REDACTED].

5.1.1.1 Common Conventions

5.1.1.1.1 Analysis Populations

The analysis populations will consist of participants as defined below:

Table 5-1 Analysis Populations

Population	Definition	Study Treatment
Screened	All screened participants who signed informed consent	—
Intent-to-Treat (ITT)	All randomized participants.	Randomized assignment
Modified Intent-to-Treat (mITT)	All randomized patients who received at least 1 dose of IP (ubrogapant) and had at least 1 posttreatment efficacy assessment in this study. The mITT population is only defined for the ubrogapant arms, as no posttreatment efficacy measurements will be collected from patients in the usual-care arm.	Randomized assignment
Safety	The Safety population is defined separately below for the ubrogapant arms and the usual-care arm. Ubrogapant arms: All randomized patients who received ≥ 1 dose of treatment. Usual care arm: All randomized patients in the usual-care arm. The purpose of the usual care arm is to contextualize any safety findings that may occur in the ubrogapant treated patients over the course of 12 months. As such, data from all patients randomized to the usual care arm, regardless of whether the patient used medication to treat migraine, will be included in the safety analyses.	Actual received

5.1.1.1.2 Study Treatments

The following treatment groups are defined for this study:

- Usual Care
- Ubrogепant 50 mg
- Ubrogепant 100 mg

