2.2 Clinical Hypothesis

Ubrogepant 50 and 100 mg is safe and tolerable for the acute treatment of migraine over 1 year.

3. Study Design

This multicenter, randomized, open-label, 52-week extension study will enroll approximately 1200 patients from approximately 200 centers in the United States. Patients will be randomized (1:1:1) to 1 of the following 3 treatment groups: usual care, ubrogepant 50 mg, or ubrogepant 100 mg (400 patients per arm). The study is open-label; however, randomization to the ubrogepant arms (50 and 100 mg) will be blinded. If and when an interim analysis occurs, the doses will be unblinded (see Section 7.6).

Patients randomized to either of the ubrogepant arms will treat up to 8 migraine attacks (of any pain severity) per 4-week period at home for a total of 1 year. Patients have the option to take a second dose of ubrogepant or rescue medication if the patient has either a nonresponding migraine or a migraine recurrence. The second dose of ubrogepant will be identical to the first dose. For detailed information on migraine treatment regimens, including optional second dose and rescue medication, see Section 5.6.

Patients randomized to the usual-care arm will be instructed to treat their migraine with medication(s) that they routinely use to relieve a migraine attack. Their usual medication(s)

for acute treatment will be identified at Visit 1 and any changes throughout the study will be recorded in the electronic case report form (eCRF).

[REDACTED]

The primary outcome is safety and tolerability. The planned safety assessments include collection of AEs, clinical laboratory determinations, ECGs, vital sign measurements, physical examinations, and the Columbia-Suicide Severity Rating Scale (C-SSRS).

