4.1 Number of Patients

Approximately 1200 patients will be randomized (400 patients per arm) from approximately 200 centers in the United States.

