7.1.2 Safety Population

The Safety population will be defined separately for the ubrogepant arms and the usual-care arm.

- Ubrogepant arms: All randomized patients who received ≥ 1 dose of treatment
- Usual-care arm: All randomized patients in the usual-care arm.

The purpose of the usual-care arm is to contextualize any safety findings that may occur in the ubrogepant treated patients over the course of 12 months. As such, data from all patients randomized to the usual-care arm, regardless of whether the patient used medication to treat migraine, will be included in the safety analyses.

[REDACTED]

[REDACTED]

[REDACTED]

[REDACTED]

[REDACTED]

[REDACTED]

[REDACTED]

[REDACTED]

[REDACTED]

[REDACTED]

[REDACTED]

- | [REDACTED]
- | [REDACTED]
- | [REDACTED]
- | [REDACTED]
- | [REDACTED]
- | [REDACTED]
- | [REDACTED]
- | [REDACTED]
- | [REDACTED]
- | [REDACTED]
- | [REDACTED]
- | [REDACTED]

[REDACTED]
[REDACTED]
[REDACTED]

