5.1.1.1.3 Statistical Methodology

The methodologies defined below apply as specified to individual endpoints defined in this SAP. All statistical tests will be 2-sided hypothesis tests performed at the 5% level of significance for main effects. All confidence intervals will be 2-sided 95% confidence intervals, unless stated otherwise.

Table 5-2 Statistical Methodology

Methodology	Description
M1 Categorical counts	
 • Number of participants in individual categories 
 ○ Participants with ≥ 1 qualifying event counted once per individual category
M2 Categorical descriptives	
 • Number and percentage of participants in individual categories 
 ○ Participants with ≥ 1 qualifying event counted once per individual category • N1 if proportion denominator \neq number of participants in the population (standard percentage denominator) 
 ○ N1 = participants with non-missing baseline value
M3 PCS descriptives	
 • Number and percentage of participants meeting potentially clinically significant (PCS) criteria 
 ○ Participants with ≥ 1 qualifying event counted once per PCS category • Percentage denominator = number of participants with all non-missing non-PCS baseline and ≥ 1 non-missing postbaseline assessment 
 ○ Unevaluable assessments considered missing
M4 Shift analysis	
 • Number and percentage of participants in individual baseline and postbaseline categories • Percentage denominator = number of participants in individual baseline categories • N1 = participants with non-missing values at both baseline and the specified postbaseline analysis visit
M5 Continuous descriptives	
 • N1, mean, standard deviation (SD), median, minimum, maximum • N1 = participants with non-missing value
M6 CFB descriptives	
 • Continuous descriptives for baseline, postbaseline, and change from baseline (CFB) values • N1 = participants with non-missing values at both baseline and the specified postbaseline analysis visit

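### The visible SAP plans no ubrogepant-versus-usual-care safety estimate with an interval and no pooled ubrogepant group, so the usual-care arm gives context only weakly

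*SAP*

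**What the plan says.** Safety and tolerability over one year is the sole stated objective (Protocol Section 2.1; SAP Table 4-1). Protocol Section 7.1.2 gives the reason for the third arm: "The purpose of the usual-care arm is to contextualize any safety findings that may occur" in ubrogepant-treated patients. Protocol Section 1 adds that open-label safety findings are hard to interpret without a comparator, and that no efficacy data are collected from usual care.

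SAP Section 5.1.1.1.2 ("The following treatment groups are defined for this study") lists three groups and no combined ubrogepant group. SAP Tables 5-20 to 5-26 present AEs, laboratory values, potential Hy's law cases, vital signs, ECGs and suicidality by group, using the descriptive methods of Table 5-2, with listings and an eDISH plot. Some disposition and baseline tables have an overall total, but it includes usual care.

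SAP Section 5.1.1.1.3 sets a convention, "All confidence intervals will be 2-sided 95% confidence intervals, unless stated otherwise", but applies methods only where an endpoint calls for them, and no visible safety endpoint does. The one method in Table 5-2 with an interval, the mixed logistic model (M8), is for efficacy and compares time intervals within each ubrogepant dose.

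One TEAE display in Table 5-20 is limited to events at or above 2% in a ubrogepant dose group and more frequent than on placebo. Placebo tablets are used for dose blinding (Protocol Sections 5.1 and 5.6.1), but there is no placebo group.

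**The concern.** A third of the patients are randomized to an arm included so that ubrogepant safety findings can be read against something. When the percentages differ between arms, the planned tables do not show how much of the gap could be chance. The only between-group rule in the AE tables refers to a group that does not exist, so it cannot be applied as written.

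The missing pooled column matters most for rare events. Protocol Section 1 reports that two earlier compounds with this mechanism were stopped for ALT increases, and Section 3.1 sets up adjudication of ALT/AST elevations. If such events are few, two separate dose columns make the drug-level question harder to read. The interim trigger already counts ubrogepant patients across both doses (SAP Section 5.1.1.6). The interim repeats all SAP analyses except efficacy, so it inherits the same gap.

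**Working it through.** **Inputs**
- 400 patients per arm, three arms, about 1200 in total (Protocol Section 4.1). Allocation (Protocol Section 3): "Patients will be randomized (1:1:1) to 1 of the following 3 treatment groups".
- Two-sided 95% intervals (SAP Section 5.1.1.1.3).
- Event risks: neither document gives any, so 1%, 2%, 5% and 10% are assumed, equal in both groups.

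**The plan's own figure.** 3 × 400 = 1200, which agrees. No power, event rate or margin is visible, so there is no sample-size formula to reproduce.

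**Step 1: zero events observed.** The one-sided 95% upper bound is 1 − 0.05^(1/n).
- One dose, n = 400: 1 − 0.05^(1/400) = 0.746%.
- Both doses, n = 800: 1 − 0.05^(1/800) = 0.374%.

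**Step 2: difference from usual care.** The half-width is 1.96 × √[p(1 − p)(1/n₁ + 1/n₂)].
- At p = 1%, 400 v 400: 1.96 × √(0.0099 × 0.005) = 1.38 points.
- At p = 1%, 800 v 400: 1.96 × √(0.0099 × 0.00375) = 1.19 points.

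| Assumed risk | One dose v usual care | Pooled v usual care |
|---|---|---|
| 1% | ±1.38 | ±1.19 |
| 2% | ±1.94 | ±1.68 |
| 5% | ±3.02 | ±2.62 |
| 10% | ±4.16 | ±3.60 |

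The ratio is √(0.00375/0.005) = 0.866 at every risk, so pooling narrows the interval by 13.4%.

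**Step 3: what an interval adds.** Take assumed counts of 4% on ubrogepant and 2% on usual care (Newcombe intervals).
- 16/400 v 8/400: +2.0 points, 95% CI −0.43 to 4.59.
- 32/800 v 8/400: +2.0 points, 95% CI −0.22 to 3.87.

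Percentages of 4% and 2% side by side do not show that either contrast is compatible with no difference. Power of a two-sided 5% test for 2% v 4% is 38% for one dose and 44% pooled, so estimation suits these data better than testing.

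**Step 4: number of intervals.** Five outcomes × three contrasts = 15. With no true effect and nominal coverage, 15 × 0.05 = 0.75 would be expected to exclude zero by chance.

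**The case against.** The protocol promises context and not a formal comparison. Its summary gives controls as not applicable, Section 5.2 says there is no control treatment, and the hypothesis in Section 2.2 is non-comparative and names both doses. Side-by-side rates from a concurrent randomized arm do give context, and dose columns match the hypothesis. This stands. A reader might infer that the arm cannot do its stated job; the documents support only that it does so weakly.

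A reader might also infer that safety is shown only as percentages. It is not: laboratory, vital-sign and ECG data also get change-from-baseline summaries, laboratory and ECG data get shift tables, and liver cases get adjudication results and plots.

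The arms do not overlap, so anyone with the published counts can add the two doses and compute a crude difference. No information is lost. What the plan lacks is a method and an outcome list fixed before the data are seen.

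A tempting argument is that pooling raises the chance of seeing a rare case. At an assumed 0.2% risk, 1 − 0.998^400 = 55% and 1 − 0.998^800 = 80%. That chance depends on how many patients are exposed, not on table columns, so it does not support the change.

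An interval would also not make the contrast clean. The Safety population takes only dosed patients in the ubrogepant arms but everyone randomized to usual care (SAP Table 5-1). AE reporting is open-label against usual care, and the medication restrictions in Protocol Sections 4.5.1 and 4.5.2 apply only to ubrogepant patients. These limits stand and must be stated beside the estimates.

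Finally, SAP Section 4 puts table specifications in a separate document, and parts of the public text are redacted or absent. A pooled column could be there. An estimator and interval method would belong in the SAP, whose safety section is largely visible.

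**Conclusion.** The point holds as a cheap improvement and not as a failure of the plan. In the visible SAP, no safety endpoint has a ubrogepant-versus-usual-care estimate with an interval, and no pooled ubrogepant group is defined. Pooling halves the zero-event bound but narrows difference intervals only modestly. The larger gain for the contrast with usual care is to show an interval at all.

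The figures assume the planned 400 per arm and, for the differences, assumed equal risks. If some ubrogepant patients never dose, the Safety population will be smaller and the intervals slightly wider. The statement about the pooled column is limited to the visible text. The placebo wording in Table 5-20 is an error whatever the shells contain.

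**What to change.** - Keep the two dose columns and add a pooled ubrogepant column to the main safety tables.
- For a fixed list (any TEAE, on-therapy SAE, AE leading to discontinuation, ALT or AST at least 3 × ULN, hepatic injury TEAEs), report Miettinen-Nurminen risk differences with 95% intervals for each dose and for pooled ubrogepant versus usual care. Label them descriptive, with no tests and no multiplicity adjustment.
- State beside them the unequal Safety population definition and the open-label AE reporting. Repeat the key differences in all randomized patients (the ITT population of SAP Table 5-1) as a check.
- In Table 5-20, replace placebo with a group that exists in this study.

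This uses data already planned for collection and costs SAP wording and a few table columns. There are two downsides. Pooling can mask a dose effect, which is why the dose columns stay. Some intervals may exclude zero by chance, which is why the list is short and the label descriptive.

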5.1.1.1.3 Statistical Methodology

The methodologies defined below apply as specified to individual endpoints defined in this SAP. All statistical tests will be 2-sided hypothesis tests performed at the 5% level of significance for main effects. All confidence intervals will be 2-sided 95% confidence intervals, unless stated otherwise.

Table 5-2 Statistical Methodology

Methodology	Description
M1 Categorical counts	
 • Number of participants in individual categories 
 ○ Participants with ≥ 1 qualifying event counted once per individual category
M2 Categorical descriptives	
 • Number and percentage of participants in individual categories 
 ○ Participants with ≥ 1 qualifying event counted once per individual category • N1 if proportion denominator \neq number of participants in the population (standard percentage denominator) 
 ○ N1 = participants with non-missing baseline value
M3 PCS descriptives	
 • Number and percentage of participants meeting potentially clinically significant (PCS) criteria 
 ○ Participants with ≥ 1 qualifying event counted once per PCS category • Percentage denominator = number of participants with all non-missing non-PCS baseline and ≥ 1 non-missing postbaseline assessment 
 ○ Unevaluable assessments considered missing
M4 Shift analysis	
 • Number and percentage of participants in individual baseline and postbaseline categories • Percentage denominator = number of participants in individual baseline categories • N1 = participants with non-missing values at both baseline and the specified postbaseline analysis visit
M5 Continuous descriptives	
 • N1, mean, standard deviation (SD), median, minimum, maximum • N1 = participants with non-missing value
M6 CFB descriptives	
 • Continuous descriptives for baseline, postbaseline, and change from baseline (CFB) values • N1 = participants with non-missing values at both baseline and the specified postbaseline analysis visit
M7 Responder	
 • Categorical descriptives using proportions for responders and nonresponders 
 ○ Nonresponders include: 
 ▪ Participants who do not meet responder criteria • N1 = all participants unless otherwise specified
M8 Logistic regression model	
 • Measures the relationship between the binomial dependent variable (number of events among number of treated attacks) and independent variables: 
 ○ fixed effect terms: 
 ▪ treatment (ubrogепant 50 mg, ubrogепant 100 mg) ▪ time ▪ treatment-by-time interaction ○ Random effect term: 
 ▪ patient

Methodology	Description
	
 • Odds ratio for comparing the percentage of treated attacks with PF at 2 hours for a given 3-month interval with that for the first 3-month interval and its 95% confidence interval will be derived from the mixed logistic regression model for each of the 2 ubrogapant treatment groups. 
 ○ Calculate two-sided p-values

CFB = change from baseline.

Raw and derived data listings will be provided, and will be fully defined in the table, figure, and data listing specification document.

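### M8 lists only a random patient effect, so the interval odds-ratio CIs will be too narrow if a patient's response varies between 3-month intervals

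*SAP*

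**What the plan says.** SAP section 5.1.1.1.3, Table 5-2, method M8, models a "binomial dependent variable (number of events among number of treated attacks"). The fixed effects are treatment (the two ubrogepant doses), time and "treatment-by-time interaction". Under "Random effect term" the table lists patient and nothing else. It does not use the word intercept, but a random intercept is the natural reading.

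The result taken from the model is the "Odds ratio for comparing the percentage of treated attacks with PF at 2 hours for a given 3-month interval" and the text continues "with that for the first 3-month interval and its 95% confidence interval will be derived from the mixed logistic regression model", separately for each ubrogepant arm. The table then adds: "Calculate two-sided p-values". The same section sets the general rule: "All statistical tests will be 2-sided hypothesis tests performed at the 5% level of significance for main effects". Confidence intervals are two-sided 95%.

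M8 is the only inferential efficacy model that can be read; M7 is descriptive. The readable text has no patient-by-interval effect, random slope, covariance structure, overdispersion parameter or empirical variance. It also gives no figure for how much a patient's response changes between intervals.

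**The concern.** A later-versus-first comparison is largely a within-patient contrast. A single patient effect raises or lowers all of a patient's intervals together, so it largely cancels. Two sources of error remain: binomial noise in the attack counts, and any change in the patient's own pain-free probability from one interval to the next. With only a random patient intercept and a model-based variance, the second source is fixed at zero.

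The documents give some reason to doubt zero. Treatment lasts 52 weeks, attacks of any pain severity may be treated (Protocol 5.6.1), so a patient's mix of attacks can shift, and concomitant medication may change between visits (Protocol 8.7). On the other side, Protocol 4.5.1 asks that migraine prophylaxis stay at a constant dose.

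If the variation is present, a chance difference between intervals is more likely to be labelled a waning or growing response, and a CI close to 1 looks more precise than it is.

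**Working it through.** The plan has no readable figure to reproduce: no power, response-rate or variance calculation for M8 can be seen. The check asks how a model of this form behaves when there is no true time effect.

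**Inputs from the documents.** One arm of 400 patients (SAP 4.1). Four 3-month intervals, hence three contrasts per arm. Two-sided 5% tests and 95% CIs (SAP 5.1.1.1.3). At most 8 treated attacks per 4 weeks, which is 8 × 13/4 = 26 per 13-week interval. The lower attack rate of 2 per month, about 6 per interval, is borrowed from the interim-analysis trigger (SAP 5.1.1.6) as a scenario only.

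**Assumptions not in the documents.** Pain-free rate of 22% for a typical patient; between-patient SD 1.0 on the logit scale; mean of 2 or 4 treated attacks per month, varying between patients; no dropout; patient-by-interval SD, written s, of 0 to 1.0.

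**Closed form.** With m attacks per interval and v = p(1-p) = 0.22 × 0.78 ≈ 0.17, the binomial variance of a patient's interval logit is about 1/(mv). Patient-by-interval variation adds s². The ratio of true to model standard error is therefore about

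r = √(1 + m·v·s²), and the actual error is 2[1 − Φ(1.96/r)].

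At s = 0.5:
- m = 6: r = √(1 + 6 × 0.17 × 0.25) = √1.255 = 1.12; error 8.0%.
- m = 12: r = √1.51 = 1.23; error 11.1%.
- m = 24 (near the cap): r = √2.02 = 1.42; error 16.8%.

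**Simulation.** The random-intercept binomial model was fitted by Gauss-Hermite maximum likelihood with Wald tests. There were 600 runs × 3 contrasts per scenario (Monte Carlo error about 0.5 to 1 point). In brackets: true SD divided by mean model SE.

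| s | M8, 2/month | M8, 4/month | Closed form, m = 6 / 12 | Sandwich, 2 / 4 per month |
|---|---|---|---|---|
| 0 | 5.2% (1.01) | 4.9% (1.00) | 5.0% / 5.0% | 5.7% / 4.9% |
| 0.25 | 7.7% (1.08) | 7.8% (1.10) | 5.7% / 6.5% | 6.2% / 5.6% |
| 0.5 | 8.3% (1.16) | 12.1% (1.24) | 8.0% / 11.1% | 5.4% / 4.2% |
| 0.75 | 12.7% (1.27) | 18.9% (1.51) | 11.8% / 18.1% | 4.3% / 4.8% |
| 1.0 | 18.4% (1.49) | 27.1% (1.79) | 16.8% / 26.1% | 5.9% / 5.1% |

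CI coverage is 100% minus the M8 error, so it runs from about 95% down to 73%. The closed form agrees from s = 0.5 upward; at s = 0.25 it is 1 to 2 points lower, so the 8% there is at the upper end.

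A second simulation with other assumptions (350 patients, 30% leaving by one year, pain freedom about 25%, last interval versus first, 400 trials) gave 5%, 8%, 13% and 23% at s = 0, 0.3, 0.5 and 0.8 with 10 attacks per interval, and 4%, 9%, 9% and 15% with 6. Patient-level robust standard errors gave 5-8%.

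**Adding a patient-by-interval random effect** (100 runs × 3 contrasts, Monte Carlo error about 1.5 points):

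| Attacks/month, s | Error, M8 | Error, added effect | Mean SE, M8 to added effect |
|---|---|---|---|
| 2, 0.5 | 6.0% | 4.3% | 0.0722 to 0.0852 (×1.18) |
| 4, 0.5 | 14.3% | 7.0% | 0.0510 to 0.0660 (×1.29) |
| 4, 1.0 | 28.3% | 6.3% | 0.0500 to 0.0948 (×1.90) |

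Around an odds ratio of 1, exp(±1.96 × SE) moves from 0.90-1.11 to 0.88-1.14 in the second row, and from 0.91-1.10 to 0.83-1.20 in the third.

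**The case against.** The strongest reply is that nothing in the documents shows the variation exists. At s = 0 the model is correctly calibrated, and at s = 0.25 the inflation is modest. A reader might infer that every interval standard error in this plan is understated; the documents do not support that. This stands, and it makes the point conditional.

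Second, Table 5-2 is a general list of methods applied as specified to individual endpoints. The endpoint-level efficacy text, which would lie between SAP 5.1.1.2.8 and 5.1.1.4, is redacted, as are the efficacy analyses in Protocol 7.3 and the software in SAP 5.1.1. A covariance structure or empirical variance could be specified there. This also stands: the point concerns M8 as it can be read. Still, Table 5-2 is where the model terms are set out, and it names one random term.

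Third, the stakes are small. The objective and primary outcome are safety and tolerability, usual care contributes no post-treatment efficacy data, and the interim analysis leaves efficacy out. A reader might infer that the sponsor will offer these CIs as proof of a stable effect, or that the trial's main conclusion is at risk. No readable passage states such a use, and no readable decision rule depends on these odds ratios.

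The objection does not remove the mechanism, or the fact that protection costs little.

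**Conclusion.** The point holds in conditional form. As readable, M8 leaves no room for patient-specific change between intervals. If such change exists, the CIs for the later-versus-first odds ratios will be too narrow and their p-values too small, more so the more attacks a patient treats per interval. With 2 to 4 treated attacks per month, the actual error of a 5% test is about 5% at a patient-by-interval SD of 0, about 8% at 0.25, 8-12% at 0.5 and 18-27% at 1.0.

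These figures rest on assumed response and attack rates, on a random-intercept reading of the patient term, and on one arm without dropout. The SD itself is unknown, so the effect could be anything from none to large. Severity is low: the analysis is within-arm and non-primary, in a study whose conclusions rest on safety.

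**What to change.** Keep the M8 terms and add one sentence to Table 5-2: the CIs and p-values for the interval odds ratios use an empirical (sandwich) variance clustered on patient. If the redacted efficacy text already specifies this or an equivalent, a cross-reference from M8 is enough.

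The cost is a line of SAP text and of code. Point estimates do not change. When there is no patient-by-interval variation almost nothing is lost (error 4.9-5.7% at s = 0); when there is, the CIs widen as they should, and the error was 4.2-6.2% across all ten simulated scenarios in the first table.

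A model with an added patient-by-interval random effect can serve as a sensitivity analysis. It is the less clean choice for the main result: it changes the conditional odds ratio being estimated and may be harder to fit when patients treat few attacks per interval.
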